	MNAR	For tipping point analyses specifically: Supplementary analysis systematically assessing scenarios which deviate from MAR or MCAR assumption	For tipping point analyses specifically: Supplementary analysis systematically assessing scenarios which deviate from MAR or MCAR assumption
	MCAR	Clinical Other Efficacy endpoints: not imputed	Clinical Other Efficacy endpoints: not imputed

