1. **Missing data for any reason** will be assumed to be MAR. The data is not explicitly imputed, but is accounted for in the analysis model.

Handling Rules for Missing Binary Data for Adjusted Composite Estimand

1. Missing data due to Natural Disaster (caused site closure, site access restrictions, or lockdowns) or Major Disruption will be assumed to be MAR. The data is not explicitly imputed, but is accounted for in the analysis model.
2. Missing data due to not entering LTE for reasons OTHER THAN lack of efficacy, worsening of PSA will be assumed to be MAR. The data is not explicitly imputed, but is accounted for in the analysis model.
3. Missing data for any other reason will be assumed to be MAR but conservatively imputed as NR

Analysis Testing for Adjusted Composite Estimand

Statistical comparison between a guselkumab group (100 mg q4w or 100 mg q8w) and the placebo group will be performed by visit through Week 24 using the Mixed-Effect Model Repeated Measures (MMRM) model for continuous endpoints and the Generalized Linear Mixed Model (GLMM) for binary response endpoints (see Section 6.13). No treatment comparison will be performed after Week 24. For continuous endpoints, only descriptive summaries and LSmeans by study intervention and visit will be presented after Week 24 through Week 156; for binary endpoints, only descriptive summaries and model based response rates by study intervention and visit will be presented after Week 24 through Week 156.

ICE Strategies for Treatment Policy Estimand

For the Treatment Policy Estimand, the occurrence of ICEs is considered irrelevant. This estimand looks at the effect of assignment to intervention group irrespective of changes to background PsA medications, study intervention adherence, or study retention.

Handling Rules for Missing Data for Treatment Policy Estimand

1. **Missing data for any reason** will not be imputed, assumed to be MCAR.

Analysis Testing for Treatment Policy Estimand

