A corresponding supportive analysis will be conducted using the Treatment Policy Estimand. For these analyses, the mFAS-UKR analysis set or further subset (if specified) will be used. For visits through Week 24, an ANCOVA model will be used for continuous endpoints, and the CMH test for treatment difference and 95% CI calculated based on Wald statistics will be used for the binary response endpoints. No treatment comparison will be performed after Week 24. For continuous endpoints, only descriptive summaries and LSmeans by study intervention and visit will be presented after Week 24 through Week 156; for binary endpoints, only descriptive summaries of response rates by study intervention and visit will be presented after Week 24 through Week 156.

Table 10 summarizes the analyses for supportive efficacy endpoints related to reduction of signs and symptoms and physical function, the methods for analyses, and the data handling rules used.

Table 10: Summary of Estimands, Analysis Sets, Data Handling Rules, and Analysis Methods for Endpoints of Signs & Symptoms and Physical Function

	Endpoint	Analysis Set	Missing Data Rules	Analysis Methods
ENDPOINTS BY VISIT THROUGH WEEK 24 AT WEEK-24 DBL, ADJUSTED COMPOSITE ESTIMAND				
1	Proportions of participants with ACR 20, ACR 50, and ACR 70 response	mFAS	NRI for MAR not due to Natural Disaster or Major Disruption	
 • Summarized descriptively • Response rates, and treatment difference in response rates and 95% CI and pvalue, based on GLMM

Table 10: Summary of Estimands, Analysis Sets, Data Handling Rules, and Analysis Methods for Endpoints of Signs & Symptoms and Physical Function

	Endpoint	Analysis Set	Missing Data Rules	Analysis Methods
2	ACR components	mFAS	-	
 Summarized descriptively LS mean (95% CI) for each intervention group
3	Change from baseline in ACR components	mFAS	-	
 Summarized descriptively LS mean (95% CI) for each intervention group
4	Percent change from baseline in ACR components	mFAS	-	
 Summarized descriptively LS mean (95% CI) for each intervention group
5	Change from baseline in HAQ-DI score	mFAS	-	
 Summarized descriptively LS mean (95% CI) for each intervention group, LS mean difference (95% CI) and p-values for differences between groups based on MMRM

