21	Proportion of participants who maintained an ACR 20 response at Week 156	mFAS who achieved an ACR 20 response at Week 24	NRI for MAR not either: due to Natural Disaster or Major Disruption, OR not enter LTE due reason other than Lack of Efficacy/Worsening PsA	
 Summarized descriptively Response rates by intervention group based on GLMM
22	Proportion of participants who maintained an ACR 50 response at Week 156	mFAS who achieved an ACR 50 response	NRI for MAR not either: due to Natural Disaster or Major Disruption, OR not enter LTE due reason other than Lack of	
 Summarized descriptively Response rates by intervention group based on GLMM

Table 10: Summary of Estimands, Analysis Sets, Data Handling Rules, and Analysis Methods for Endpoints of Signs & Symptoms and Physical Function

	Endpoint	Analysis Set	Missing Data Rules	Analysis Methods
		at Week 24	Efficacy/Worsening PsA	
23	Proportion of participants who maintained an ACR 70 response at Week 156	mFAS who achieved an ACR 70 response at Week 24	NRI for MAR not either: due to Natural Disaster or Major Disruption, OR not enter LTE due reason other than Lack of Efficacy/Worsening PsA	
 Summarized descriptively Response rates by intervention group based on GLMM
24	Proportion of participants who maintained HAQ-DI response at Week 156	mFAS who achieved HAQ-DI response at Week 24	NRI for MAR not either: due to Natural Disaster or Major Disruption, OR not enter LTE due reason other than Lack of Efficacy/Worsening PsA	
 Summarized descriptively Response rates by intervention group based on GLMM

**ENDPOINTS BY VISIT THROUGH WEEK 24 AT WEEK-24 DBL,
AFTER WEEK 24 THROUGH WEEK 48 AT WEEK-48 DBL,
AFTER WEEK 48 THROUGH WEEK 96 AT WEEK-96 DBL, AND
AFTER WEEK 96 THROUGH WEEK 156 AT FINAL DBL, USING TREATMENT POLICY
ESTIMAND AND THE mFAS-UKR ANALYSIS SET INSTEAD OF mFAS**

- The endpoints analyzed using the Adjusted Composite Estimand for corresponding visits/DBL are repeated here, except:
 - No imputation will be applied and all analyses will be based on observed data
 - Continuous endpoints will use ANCOVA instead of MMRM; binary response endpoints will use CMH test with CI based on Wald statistics instead of GLMM for visits up to and including Week 24

[figure not shown]
[figure not shown]

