The same estimands defined in Section 5.3.6.1 will be used for WPAI.

Method of Analysis

The same methods of analysis for the Other Efficacy endpoints related to reduction of signs and symptoms and physical function in Section 5.3.6.2.10 will also be used for WPAI.

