6.13. Appendix 13: Description of Statistical Models

MMRM Model

To account for the missing data for continuous endpoints, an MMRM model will be used on the change from baseline, under the assumption of MAR, to test the difference between a guselkumab group and the placebo group. The model will include treatment group, the interaction terms of visit with treatment group, randomization strata levels, and baseline score as explanatory variables. An unstructured covariance matrix for repeated measure within a subject will be used. The F-test will use Kenward-Roger's approximating for degree of freedom. In case of lack of convergence, empirical structured covariances will be used in the following order until convergence is reached: 1) Toeplitz 2) first order Autoregressive Moving Average. For analyses through Week 24 the model will include data from all 3 treatment groups through Week 24. The treatment difference between a guselkumab group and the placebo group will be estimated by the difference in the least squares means (LSmeans). The 95% confidence interval (CI) for the differences in LSmeans and p-values will be calculated based on the MMRM.

After Week 24, the MMRM model may still be used to generate LSmeans for each treatment group. However, LSmeans difference between treatments and associated p-values will no longer be calculated.

ANCOVA Model

The ANCOVA model will be used on the change from baseline, under the assumption of MCAR, to test the difference between a guselkumab group and the placebo group. The model will include treatment group, randomization strata levels, and baseline score as explanatory variables. For analyses through Week 24 the model will include data from all 3 treatment groups at Week 24. The treatment difference between a guselkumab group and the placebo group will be estimated by the difference in the least squares means (LSmeans). The 95% confidence interval (CI) for the differences in LSmeans and p-values will be calculated based on ANCOVA.

After Week 24, the ANCOVA model may still be used to generate LSmeans for each treatment group. However, LSmeans difference between treatments and associated p-values will no longer be calculated.

GLMM

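### Supportive Treatment Policy analyses of the other non-radiographic endpoints assume MCAR, where the SAP's own MAR methods would relax that assumption at little cost (minor)

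*SAP*

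**What the plan says.** SAP 5.3.6.2.10 sets out two analyses of the other clinical endpoints.

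- **Main analysis (Adjusted Composite Estimand).** It uses the "Mixed-Effect Model Repeated Measures (MMRM) model for continuous endpoints and the Generalized Linear Mixed Model (GLMM) for binary response endpoints" and treats missing data as MAR. For binary endpoints, part of the missing data is then set to non-response by convention.
- **Supportive analysis (Treatment Policy Estimand, mFAS-UKR).** Missing data for any reason "will not be imputed, assumed to be MCAR". The method is: "For visits through Week 24, an ANCOVA model will be used for continuous endpoints, and the CMH test for treatment difference and 95% CI", with Wald intervals for binary endpoints.

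The supportive rule recurs elsewhere. Table 6 (SAP 5.3.2) has, in its Treatment Policy MCAR row, "Clinical Other Efficacy endpoints: not imputed" for both continuous and binary endpoints. Table 10 states "No imputation will be applied and all analyses will be based on observed data" and "Continuous endpoints will use ANCOVA instead of MMRM". Tables 11, 12 and 13 carry the same lines for skin, nails and quality of life. SAP 5.5.5 brings in work productivity by reference, since the methods "in Section 5.3.6.2.10 will also be used for WPAI". Appendix 13 (SAP 6.13) ties the model to the assumption: "The ANCOVA model will be used on the change from baseline, under the assumption of MCAR". Its covariates are treatment, randomization strata and baseline score.

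SAP 5.3.6 makes all p-values for these endpoints nominal and limits treatment comparisons to Week 24.

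**The concern.** The Treatment Policy Estimand is described as the effect of being assigned to a group whatever happens to background medication, adherence or staying in the study. Its analysis at each visit nevertheless uses only those assessed at that visit, on the assumption that absence is unrelated to outcome. If people who are doing badly at, say, Week 16 are more likely to miss Week 24, observed-case ANCOVA and CMH make no use of the Week 16 value. The estimate can then be biased. A likelihood model over all visits, or imputation from earlier visits, does use that information. At stake is how well these supportive results show the effect regardless of intercurrent events.

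**Working it through.** **1. The passages side by side.** The plan states no figure on this point, so there is none to reproduce. Its assumptions can be compared.

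- SAP 5.3.6.2.10, same endpoints, Adjusted Composite Estimand: missing data MAR.
- SAP 5.3.4.4, Supplementary Analysis 1 (ACR 20, Treatment Policy, mFAS-UKR): MAR, FCS MI.
- SAP 5.3.5.2, Supplementary Analysis 1 (modified vdH-S, Treatment Policy, mFAS-UKR): MAR, FCS MI. The version history records that version 3 moved this analysis from MCAR without imputation, giving regulatory feedback as the reason.
- SAP 6.11, Table 17, footnote c: the ACR components enter the modified vdH-S imputation because they might be connected with why data are missing. That is outcome-related missingness, which MCAR rules out.
- SAP 5.3.6.2.10, other endpoints, Treatment Policy: MCAR, with no reason given.

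One result is that ACR 20 at Week 24 has two Treatment Policy analyses in mFAS-UKR: the imputed one in 5.3.4.4 and the observed-case one from the Treatment Policy block of Table 10, which repeats row 1. The SAP does not say which one leads.

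**2. Binary illustration.** True rates of 60% and 35% are the planning values in SAP 3.1.1. The missingness rates are assumed. If responders are missing with probability r and non-responders with probability n, the observed-case rate is p(1-r) / [p(1-r) + (1-p)(1-n)].

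With r = 5% and n = 20%:

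- guselkumab: 0.570 / (0.570 + 0.320) = 64.0%
- placebo: 0.3325 / (0.3325 + 0.520) = 39.0%

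With r = n = 5% the true rates are returned.

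| Non-responders missing 20% (all others 5%) | Missing, guselkumab / placebo | Observed rates | Difference (true 25.0) |
|---|---|---|---|
| Both arms | 11.0% / 14.75% | 64.0% vs 39.0% | 25.0 points |
| Placebo only | 5.0% / 14.75% | 60.0% vs 39.0% | 21.0 points |
| Guselkumab only | 11.0% / 5.0% | 64.0% vs 35.0% | 29.0 points |

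Under the same rule in both arms, the odds in each arm are multiplied by 0.95/0.80, so the odds ratio is exactly preserved. The risk difference stays at 25.0 because these two rates lie roughly evenly around one half. At other rates it could shift somewhat.

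**3. Continuous illustration.** All inputs are assumed: 350 per arm, baseline plus six post-baseline visits, correlation 0.7, true final difference -0.40 SD, 400 runs, Monte Carlo error 0.003. Dropout at each visit from the second onwards is logistic, either random or dependent on the last observed change or on baseline. Complete-case ANCOVA adjusts for baseline. The MAR estimate is a sequential regression on all earlier visits, standing in for an unstructured MMRM.

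| Dropout depends on | Missing, guselkumab / placebo | ANCOVA | MAR estimate | ANCOVA bias |
|---|---|---|---|---|
| Nothing (random) | 9% / 9% | -0.403 | -0.402 | within error |
| Baseline only | 20% / 20% | -0.403 | -0.403 | within error |
| Response, same rule in both arms | 9% / 12% | -0.388 | -0.396 | 0.012 |
| Response, same rule in both arms | 19% / 23% | -0.386 | -0.399 | 0.014 |
| Response, same rule in both arms | 33% / 41% | -0.377 | -0.406 | 0.023 |
| Response, placebo only | 12% / 23% | -0.329 | -0.401 | 0.071 |

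Bias is the ANCOVA estimate minus -0.40; for the last row, -0.329 + 0.400 = 0.071 SD. In these continuous scenarios it shrinks the effect. The MAR estimate does well because the simulated dropout depends only on observed values, so MAR holds by construction. The table shows what the ANCOVA loses under MAR; it does not show that MAR is true in this trial.

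**The case against.** The strongest reply is that nothing decisive rests on these analyses. They are supportive, with nominal p-values, and outside the four-hypothesis fixed sequence. The main analysis of the same endpoints already uses MMRM and GLMM. Both confirmatory endpoints have Treatment Policy analyses under MAR with tipping-point analyses. All of that stands and sets the severity.

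A reader might infer that these are completer analyses that discard people who stop drug. The documents do not support that. Under treatment policy, data after stopping drug or changing background medication are used. Protocol 7.2 asks participants who stop before Week 24 to attend all visits through Week 24. Early-escape participants stay on their randomized regimen with their data kept. Only participants with no assessment at a visit are lost, and ANCOVA remains valid if absence depends only on treatment, strata and baseline.

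A reader might also infer from the version 3 change that regulators asked for MAR here too. The version history names only the key secondary analysis, so that cannot be concluded.

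Finally, a MAR model without intercurrent-event rules predicts missing off-drug values partly from people still on drug, which can itself mislead under treatment policy. That is a fair caution, but it applies at least as much to the observed-case analysis, which also lets those observed speak for those missing and ignores their earlier visits.

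**Conclusion.** The point holds as a minor, inexpensive improvement. The SAP assumes MCAR for these analyses without a reason, while its own imputation footnote and its Treatment Policy analyses of the two confirmatory endpoints point to MAR. If missingness through Week 24 depends on earlier post-baseline response, the observed-case estimates can be biased.

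The documents give no dropout rate, so neither size nor direction is known. Under the assumed scenarios, bias was about 0.01 to 0.02 SD with a shared response-driven rule and 0.07 SD with response-driven dropout in placebo only. The binary difference moved by up to 4 points either way when missingness differed by arm. These figures illustrate a risk. They do not show that bias exists in this trial or that it would favour guselkumab. The primary and key secondary conclusions are not affected.

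**What to change.** For treatment comparisons through Week 24 under the Treatment Policy Estimand:

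1. Apply the MMRM and GLMM already specified in SAP 6.13 to all observed data, including data after intercurrent events, with no intercurrent-event rules. FCS MI, as in Supplementary Analysis 1 of the primary endpoint, is an acceptable alternative.
2. Change the assumption from MCAR to MAR in SAP 5.3.6.2.10 and Table 6, and align Tables 10 to 13. Work productivity follows by reference.
3. Keep the observed-case ANCOVA and CMH as a labelled sensitivity analysis. For ACR 20 at Week 24, say which Treatment Policy result leads.
4. State that summaries after Week 24 are descriptive observed-case results.

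The cost is some added programming and possible GLMM convergence problems, for which SAP 6.13 already gives fallback covariance structures. MAR remains an assumption. The documents do not say whether the Week 24 database lock has occurred; if it has, the added analysis should be labelled as specified after lock.

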5.3.6.3. Endpoints Related to Skin Disease

In this study, Other Efficacy endpoints for skin disease include those related to PASI, IGA, and DLQI.

All Other Efficacy endpoints related to skin disease will be conducted under the mFAS population among participants with $\geq 3\%$ body surface area (BSA) psoriatic involvement and an Investigator's Global Assessment (IGA) score of ≥ 2 (mild) at baseline for Adjusted Composite Estimand, and mFAS-UKR among participants with $\geq 3\%$ body surface area (BSA) psoriatic involvement and an Investigator's Global Assessment (IGA) score of ≥ 2 (mild) at baseline for Treatment Policy Estimand, **unless explicitly stated otherwise**.

5.3.6.3.1. PASI Related Endpoints

CCI

[figure not shown][figure not shown]

The IGA related Other Efficacy endpoints include:

- Proportion of participants with IGA response by visit over time through Week 156 among the participants with $\geq 3\%$ BSA psoriatic involvement and an IGA score of ≥ 2 (mild) at baseline.
- Proportion of participants with an IGA score of 0 (cleared) by visit over time through Week 156 among the participants with $\geq 3\%$ BSA psoriatic involvement and an IGA score of ≥ 2 (mild) at baseline.

5.3.6.3.3. DLQI Related Endpoints

CCI

The DLQI related Other Efficacy endpoints include:

- Change from baseline in DLQI score by visit through Week 156 among the participants with $\geq 3\%$ BSA psoriatic involvement and an IGA score of ≥ 2 (mild) at baseline.
- Proportion of participants who achieve a DLQI score of 0 or 1 by visit through Week 156 among the participants with baseline DLQI score >1 and with $\geq 3\%$ BSA psoriatic involvement and an IGA score of ≥ 2 (mild) at baseline.
- Proportion of participants who achieve ≥ 5 -point improvement from baseline in DLQI score by visit through Week 156 among the participants with baseline DLQI score ≥ 5 and with $\geq 3\%$ BSA psoriatic involvement and an IGA score of ≥ 2 (mild) at baseline.

5.3.6.3.4. Method of Analysis

In general, the same methods of analysis for the Other Efficacy endpoints related to reduction of signs and symptoms and physical function in Section 5.3.6.2.10 will also be used for those related to skin disease.

Table 11 summarizes the analyses for supportive efficacy endpoints related to skin disease, the methods for analyses, and the data handling rules used.

Table 11: Summary of Estimands, Analysis Sets, Data Handling Rules, and Analysis Methods for Endpoints of Skin Disease

	Endpoint	Analysis Set	Missing Data Rules	Analysis Methods
ENDPOINTS BY VISIT THROUGH WEEK 24 AT WEEK-24 DBL, ADJUSTED COMPOSITE ESTIMAND				
1	Change from baseline in PASI score	mFAS with $\geq 3\%$ BSA and IGA ≥ 2 at baseline	-	
 • Summarized descriptively • LS mean (95% CI) for each intervention group, LS mean difference (95% CI) and p-values for differences between groups based on MMRM
2	Percent change from baseline in PASI score	mFAS with $\geq 3\%$ BSA and IGA ≥ 2 at baseline	-	
 • Summarized descriptively • LS mean (95% CI) for each intervention group, LS mean difference (95% CI) and p-values for differences between groups based on MMRM
3	Proportions of participants with PASI $\geq 75\%$, $\geq 90\%$, $\geq 100\%$ improvement	mFAS with $\geq 3\%$ BSA and IGA ≥ 2 at baseline	NRI for MAR not due to Natural Disaster or Major Disruption	
 • Summarized descriptively Response rates, and treatment difference in response rates and 95% CI and pvalue, based on GLMM
4	Proportion of participants with both PASI $\geq 75\%$ improvement and ACR 20 response	mFAS with $\geq 3\%$ BSA and IGA ≥ 2 at baseline	NRI for MAR not due to Natural Disaster or Major Disruption	
 • Summarized descriptively • Response rates, and treatment difference in response rates and 95% CI and pvalue, based on GLMM

Table 11: Summary of Estimands, Analysis Sets, Data Handling Rules, and Analysis Methods for Endpoints of Skin Disease

	Endpoint	Analysis Set	Missing Data Rules	Analysis Methods
5	Proportion of participants with both PASI $\geq 75\%$ improvement and modified PsARC response	mFAS with $\geq 3\%$ BSA and IGA ≥ 2 at baseline	NRI for MAR not due to Natural Disaster or Major Disruption	
 Summarized descriptively Response rates, and treatment difference in response rates and 95% CI and pvalue, based on GLMM
6	Proportion of participants with IGA response	mFAS with $\geq 3\%$ BSA and IGA ≥ 2 at baseline	NRI for MAR not due to Natural Disaster or Major Disruption	
 Summarized descriptively Response rates, and treatment difference in response rates and 95% CI and pvalue, based on GLMM
7	Proportions of participants with IGA score of 0	mFAS with $\geq 3\%$ BSA and IGA ≥ 2 at baseline	NRI for MAR not due to Natural Disaster or Major Disruption	
 Summarized descriptively Response rates, and treatment difference in response rates and 95% CI and pvalue, based on GLMM
8	Change from baseline in DLQI score	mFAS with $\geq 3\%$ BSA and IGA ≥ 2 at baseline	-	
 Summarized descriptively LS mean (95% CI) for each intervention group, LS mean difference (95% CI) and p-values for differences between groups based on MMRM
9	Proportions of participants with DLQI score of 0 or 1	mFAS with DLQI score ≥ 1, $\geq 3\%$ BSA and IGA ≥ 2 at baseline	NRI for MAR not due to Natural Disaster or Major Disruption	
 Summarized descriptively Response rates, and treatment difference in response rates and 95% CI and pvalue, based on GLMM.
10	Proportions of participants with ≥ 5 -point improvement in DLQI score	mFAS with DLQI score ≥ 5, $\geq 3\%$ BSA and IGA ≥ 2 at baseline	NRI for MAR not due to Natural Disaster or Major Disruption	
 Summarized descriptively Response rates, and treatment difference in response rates and 95% CI and pvalue, based on GLMM.

'-' indicates no missing data rules to be applied

ENDPOINTS BY VISIT AFTER WEEK 24 THROUGH WEEK 48 AT WEEK-48 DBL, USING ADJUSTED COMPOSITE ESTIMAND

1, 2, 8	Same as through Week 24	Same as through Week 24	Same as through Week 24	
 Summarized descriptively LSMeans and 95% CI by intervention group based on MMRM model
---------	-------------------------	-------------------------	-------------------------	--

Table 11: Summary of Estimands, Analysis Sets, Data Handling Rules, and Analysis Methods for Endpoints of Skin Disease

	Endpoint	Analysis Set	Missing Data Rules	Analysis Methods
3, 4, 5, 6, 7, 9, 10	Same as through Week 24	Same as through Week 24	Same as through Week 24	
 • Summarized descriptively • Response rates by intervention group based on GLMM

ENDPOINTS BY VISIT AFTER WEEK 48 THROUGH WEEK 96 AT WEEK-96 DBL, AND AFTER WEEK 96 THROUGH WEEK 156 AT FINAL DBL, USING ADJUSTED COMPOSITE ESTIMAND

1, 2, 8	Same as through Week 24	Same as through Week 24	Same as through Week 24	
 • Summarized descriptively • LSMeans and 95% CI by intervention group based on MMRM model
3, 4, 5, 6, 7, 9, 10	Same as through Week 24	Same as through Week 24	NRI for MAR not either: due to Natural Disaster or Major Disruption, OR not enter LTE due reason other than Lack of Efficacy/Worsening PsA	
 • Summarized descriptively • Response rates by intervention group based on GLMM

ENDPOINTS BY VISIT THROUGH WEEK 24 AT WEEK-24 DBL, AFTER WEEK 24 THROUGH WEEK 48 AT WEEK-48 DBL, AFTER WEEK 48 THROUGH WEEK 96 AT WEEK-96 DBL, AND AFTER WEEK 96 THROUGH WEEK 156 AT FINAL DBL, USING TREATMENT POLICY ESTIMAND AND THE mFAS-UKR ANALYSIS SET INSTEAD OF THE mFAS

- The endpoints analyzed using the Adjusted Composite Estimand for corresponding visits/DBL are repeated here, except:
 - No imputation will be applied and all analyses will be based on observed data
 - Continuous endpoints will use ANCOVA instead of MMRM; binary response endpoints will use CMH test with CI based on Wald statistics instead of GLMM for visits up to and including Week 24

